The analysis of claims data on prescribing and use of smoking cessation medication treatment would not be possible if consent was required of all participants for access to their doctor's de-identified prescribing data. The study has enrolled 1166 participants. It is important to be able to utilize de-identified prescribing data for as many participants as possible in order to compare administrative measures (i.e., not based on self-report) of medication use across the study intervention arms to assess the effectiveness of the interventions on prescribing and the effects of medication use in this understudied population on abstinence. The funder specifically asked for these data to be included in the study, but made the request after the initial protocol was already implemented. The majority of withdrawn participants have lost agency services and would be extremely difficult to locate for consenting purposes. For participants we are able to contact, requiring consent to obtain and use de-identified pharmacy data would impose a significant participant burden. It would take approximately 30 minutes, a substantial amount of time, to explain the processes for disclosing and deidentifying the data and why this represents minimal risk.

4) Participants will be provided with additional pertinent information after participation.

At the initial meeting with the study coordinator, during the verbal consent process, participants will be provided with a fact-sheet that details important information about the study, including who can be contacted for more information. Participants will also be offered a copy of the Privacy Notice.

5) The research involves no more than minimal risk to the privacy of the participants.

This research involves no more than minimal risk to the privacy of participants. No PHI will be collected by MGH study staff. Please see above for the plan to protect identifying information from improper use and disclosure.

The use of pharmacy data involves no more than minimal risk to participants. All PHI disclosed to MassHealth will be protected using secure transfer and storage and we will disclose the minimum amount of data necessary (e.g., IDs, intervention date windows, age groups) that pose minimal risk to participants. No PHI will be included in any of the data files received from MassHealth or analyzed by MGH staff and the de-identified data will be protected (details above).

Only aggregate results across groups of providers or patients will be analyzed and shared; no information on individual providers or patients will be generated or shared. We will not publish or report any cell size with 10 or fewer participants in accordance with data suppression policies.

V. STUDY PROCEDURES

This study aims to compare the effects of service interventions, AD+CHW, AD, CHW and TAU, on smoking outcomes in a large community psychiatric rehabilitation system of care.

Allocation concealment: Intervention allocation will be randomly assigned by computer generated list.

Blinding: Neither participants nor providers will be blind to the intervention assigned. Research coordinators who conduct the surveys with all participants will be blind to intervention assignment to the extent possible as the participant may volunteer information that makes study assignment clear to the coordinator.

1. Overview of Survey Visits:

Research assistants will attend the annual, scheduled CBFS and ACT rehabilitation team treatment planning meeting in the community to conduct an annual survey when the psychiatric rehabilitation team is engaging with the patient. The schedule of psychiatric rehabilitation team meeting is fixed according to the month of enrollment in CBFS or ACT, and the study assessments will accommodate this schedule. The brief annual survey will take 5 minutes for most participants. Those who complete the baseline survey will be asked to repeat the survey at their next two annual psychiatric rehabilitation team meetings.

2. Survey Items

2.1 **Demographics:** age, sex, race, living situation (Group Home/Supervised Housing or Independent Living) (Baseline Assessment only)

2.2 **Smoking Status:** If smoking: number of cigarettes smoked per day; if prior smoker: time since last cigarette and quitting method.

2.3 **Smoking cessation services in the past year:** If smoking: report of whether smoking status was assessed by their primary care physician or nurse, whether advice to quit smoking was given, whether prescription of pharmacotherapeutic cessation aids and/or referral to behavioral smoking cessation treatment were offered or made.

- If pharmacotherapeutic cessation aids were prescribed, we will ask if the was filled, and, if so, whether the medication was used, and, if so, for how long.

- If behavioral smoking cessation support was recommended, we will ask if this support was used and, if so, what type (quit line, smoking cessation group or individual treatment) and how many sessions were attended.
- 2.4 If smoking: ***The Heaviness of Smoking Index*** (HSI) will be administered. It consists of 2 questions: time to first cigarette of the day and number of cigarettes smoked per day. The HSI and its individual items are strong predictors of quitting behavior, now validated in the International Tobacco Control cohort with 8,000 respondents/wave and 6,000 for prediction of cessation outcomes [75].
- 2.5 ***Health related quality of life***: The single item self-reported general health status question (SF-1) is well validated as a descriptor of individual health and wellbeing as well as community health status. [76] SF-1 scores are highly correlated with measures such as future health care use, mortality, disability, and mental health status [77-82] and SF-1 scores are significant indicators of health outcomes, independent of gender or racial/ethnic group. [78]
- 2.6 In those who report having quit smoking: Carbon monoxide in expired air, ***Expired CO***, will be measured with a small, hand-held CO monitor. To do so, participants will blow into a straw attached to the device, a Bedfont Smokerlyzer II (Kent, England), following a 15-second breath hold to verify self-report of non-smoking status. Expired CO <5 parts per million (ppm) is consistent with smoking abstinence.
 - We will measure cotinine in saliva in those whose expired CO is >5 ppm but report smoking zero cigarettes per day in the past 7 days and are not using nicotine replacement therapy. To do this, participants will provide a saliva sample via passive drool that will be tested with a NicAlert® dipstick (Nymox Corp., Hasbrouck Heights, NJ). The NicAlert® test displays seven zones that represent a range of cotinine levels from 0 (0–10 ng/ml) to 6 (> 1000 ng/ml). Participants that obtain a level between 1 (10–30 ng/ml) and 6 will be considered to be smoking

This is standard for biochemically verified abstinence and a critical component to obtaining reliable estimates of smoking status, the study's primary outcome, which will be used to judge the utility of the interventions being tested.

3. Interventions

As part of their ongoing care, staff in CBFS and ACT psychiatric rehabilitation programs identify those in their programs who regularly smoke tobacco and the clinics providing their medical care. In cohort 1, clinics were randomized to receive AD to their clinicians or TAU. Participants whose primary care practices were assigned to receive AD were randomized to be offered a CHW (AD+CHW) or not (AD). In cohort 2, participants were randomized to receive CHW support or TAU. These interventions are detailed below.

There will be no prescription of or distribution of any smoking cessation medication of any kind to study participants by study staff. Any prescription of or recommendation for smoking cessation medication will be done in the clinical setting by clinical treaters.

3.1. Usual care (TAU) for adults with SMI in Massachusetts consists of rehabilitation services publicly funded by the state and traditional fee for service outpatient medical and psychiatric care. Importantly, medical care is not programmatically integrated with the psychiatric rehabilitation services. Patients who receive CBFS or ACT psychiatric rehabilitation

services from the primary agencies delivering such care in the Boston area, who agree to enroll in the study and whose primary medical clinic is assigned to the TAU arm of the study will meet with a RA at three consecutive, regularly-scheduled, annual psychiatric rehabilitation team meetings for brief survey. They will receive no other study-related intervention.

3.2. Academic detailing (AD) is a targeted continuing medical education (CME) strategy that adapts social marketing techniques, using mixed interactive and didactic formats in individual and group settings integrated into the practice setting to promote beneficial changes in medical care [83]. AD helps clinicians understand and adopt targeted evidence-based practices and is one of the few Continuing Medical Education (CME) interventions that has consistently demonstrated improved alignment of physician prescribing behavior with evidence-based practice [84-86]. AD has been effective specifically in increasing provision of smoking cessation treatment in the general population and in low-income, disadvantaged areas [87-90] and to improve medication treatment for those with SMI [91]. Evidence strongly indicates that physician advice to quit, prescription of pharmacotherapeutic cessation aids, and referral for behavioral smoking cessation treatment is highly effective for smoking cessation in those with SMI. Local experts will provide structured alternatives needed to overcome strongly held but incorrect beliefs of prescribers. Brief reinforcement visits will increase success rates. AD will allow a clinical educator to engage with a prescriber, understand their practice patterns, assess their needs, and identify gaps in knowledge, and then offer specific, action-oriented recommendations to improve the quality of care.

Each prescriber working in clinics assigned to the AD intervention will be invited to a one-hour staff meeting (30-minute AD lecture and 30 minute interactive question and answer period) at which local experts, the academic detailers, will present the strong evidence base for smoking cessation treatment in those with SMI to clinic staff. Prescribers will be eligible for one hour of free Continuing Education Units (CEU) for attendance at this regularly scheduled staff meeting. To receive CEU credits, prescribers who attend this meeting will be asked to report how frequently they recommend smoking cessation treatment to their patients with SMI, to complete an evaluation of the AD session, and to rate how likely they are to increase implementation of tobacco dependence treatment to those with SMI as a result of the first AD visit (Exploratory Aim 1). This initial group AD meeting will be followed by 1 on 1 academic detailing visits with prescribers who agree that will consist of 5-10 minute targeted individual sessions with prescribers. Prescribers will be offered up to two AD visits per year for two years. Drs. [name], [name], [name] and an internal medicine fellow from the National Resource Center for Academic Detailing (NaRCAD) (<http://www.narcad.org>) at the Brigham and Women's Hospital will provide AD to prescribers at the 20-30 primary care clinics that are assigned to the AD intervention to promote implementation of evidence-based pharmacotherapeutic and behavioral smoking cessation treatment for smokers with SMI.

Evidence to be presented to prescribers by AD: AD will present the compelling evidence for efficacy and tolerability of pharmacotherapeutic cessation aids combined with behavioral treatment for smoking cessation for those with SMI [92] along with strong and growing evidence that smoking cessation is associated with improved psychiatric symptoms such as anxiety and depression [93]. The academic detailing content will focus on:

- i) The United States Preventive Services Task Force (USPSTF) recommendation, with Grade 'A' evidence, that clinicians ask all adults about tobacco use and provide cessation interventions for those who use tobacco products.

- ii) The strong evidence base for safety and tolerability of nicotine dependence treatment, specifically for smokers with SMI,
- iii) Specific information critical to safe and effective provision of smoking cessation treatment in conjunction with the multiple other medications commonly used by those with SMI,
- iv) Tools to improve effective communication with individuals with SMI.

AD will present robust evidence for efficacy for bupropion alone and in combination with nicotine replacement therapy (NRT) and the strong and growing evidence for safety and efficacy of varenicline for smoking cessation specifically in those with SMI that has emerged since the PORT Guidelines were published in 2010. AD will emphasize that, like smokers in the general population, efficacy of pharmacotherapy is enhanced by behavioral treatment, but unlike the general population, behavioral treatment alone is associated with a very low average cessation rate of 4%. AD will educate prescribers about abnormalities in brain nicotine receptors in those with schizophrenia spectrum disorders [94-96], that may confer a particular cognitive benefit from nicotine [97-100], and medications that substitute the actions of nicotine in the brain, such as NRT, bupropion [41], NRT [97, 98] and varenicline [101-103] to improve cognitive impairments associated with schizophrenia and maintain abstinence [103-106].

3.3. Community Health Worker (CHW) The CHW will offer to support patients and prescribers in health promotion and preventive care in general and specifically to support communication between the primary care provider and patient regarding smoking status, smoking cessation, and to aid implementation of any smoking cessation treatments recommended by prescribers. CHWs will complete the standard CHW certificate training program in general preventive medicine, available through the Boston Public Health Commission: www.umassmed.edu/ahec/. CHWs will then receive the following training:

- i) Evidence based, health empowerment training designed for peer specialists to improve health literacy, healthcare decision-making, and support a positive alliance with those with SMI and their prescribers. These person-centered health empowerment trainings include: a. Whole Health Action Management (WHAM), a SAMHSA-HRSA Center for Integrated Health Solutions training program funded in Massachusetts by the DMH in partnership with the Transformation Center [107] to encourage increased resiliency, wellness, and self-management of health and behavioral health among people with mental illnesses and substance use disorders [108, 109]
- ii) CHWs will complete the 2-day, accredited Tobacco Treatment Specialist (TTS) certificate program from University of Massachusetts designed for health care professionals and paraprofessionals [110].
- iii) Training with Drs. [name], [name] and [name] on the content of the AD materials being delivered to prescribers.
- iv) Orientation to the CBFS and ACT programs of psychiatric rehabilitation.
- v) Training with Drs. [name] and [name] on cognitive behavioral smoking cessation treatment for those with SMI [25, 26, 37, 111-113].

CHWs will receive weekly group supervision with supervisors and monthly group supervision with senior clinical staff to review cases, as we have done successfully in prior large intervention evaluation research projects and as is routine in the CBFS and ACT practice model. As requested by participants, each CHW will provide flexible individual support to up to 35 participants and their prescribers as follows:

- a. Partner with patients to identify their smoking-specific health goals as part of their recovery plan, using techniques emphasized in their training on tobacco treatment and health empowerment.
- b. Provide practical preparation and support for prescriber visits, including making appointments, arranging transportation, helping patients to compile an accurate medication list to bring to appointments.
- c. Provide practical assistance to patients to communicate their smoking behavior and stage of change to their prescriber and assist them in understanding the treatment options recommended by prescribers.
- d. Assist patients in obtaining recommended treatment through support obtaining prescriptions, liaison with staff who aid medication administration, and transport to smoking cessation groups.
- e. Promote communication of cessation attempts between prescribers and caregivers in the extended system of rehabilitation care in those who begin pharmacotherapies, to improve support for the cessation effort and broad monitoring and communication of any medication side effects, nicotine withdrawal symptoms and psychiatric symptom
- f. Co-lead smoking cessation groups with clinical staff with manualized content tailored to people with SMI, delivered in the psychiatric rehabilitation settings in which the individuals are served, including club houses and wellness centers. Fidelity to the CBT manual and clinical technique will be measured with a quantitative scale developed for this purpose and extensively used by our group.

4. Mixed Methods

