Randomization will be conducted by MGH statisticians and will be based on de-identified data provided by the psychiatric rehabilitation agencies about the primary care clinic and the study ID. Clinics that treat smokers with SMI who agreed to participate in the baseline survey will be randomized. Statisticians will , stratify the randomization by number of participating smokers with SMI treated at the site, Cohort 1 (AD-eligible) comprised participants with primary care clinics serving ≥ 3 enrolled participants. These clinics were randomized to receive AD to their clinicians or TAU. Participants whose primary care practices were assigned to receive AD were randomized to be offered a CHW (AD+CHW) or not (AD). Cohort 2 (AD-ineligible) comprised participants whose primary care clinic served < 3 enrolled participants who were randomized to CHW or TAU. Statisticians will create a field in the database that indicates, for each study ID, the clinic assignment (TAU or AD) and CHW assignment. These databases (one for each psychiatric rehabilitation agency) will be returned to Project Managers at the psychiatric rehabilitation service providers, for use in arranging for CHW support and scheduling of follow up surveys at annual IAP meetings. MGH will be informed of which clinics are assigned to AD for training purposes. At no time will MGH staff be given identifying information for participants.

The following staff are employees at the psychiatric rehabilitation agencies, Bay Cove and Vinfen, and will have a role in the study: [name] is co-PI for the project and medical director at Bay Cove, [name] is medical director at Vinfen and a consultant to the project, and 2 clinically trained Project Managers, [name], LICSW is employed at Bay Cove and [name] CPH, MSW, LICSW, at Vinfen.. All of the above mentioned staff will complete necessary trainings in human subjects protections. These staff will work with the CBFS teams to identify annual IAP assessment dates for smokers in their teams at which surveys could

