In order to examine the effect of the study interventions on rates of prescribing smoking cessation medication (i.e. varenicline, bupropion and nicotine replacement therapy) we will receive deidentified MassHealth pharmacy claims data for all study participants who are covered by MassHealth. To maintain the firewall between the human services agencies (Bay Cove and Vinfen) and MGH, we will use a multi-step process to obtain deidentified claims data from MassHealth. First, the human services agencies will send MassHealth a file that contains participants' Study IDs linked with MassHealth ID. Next, MGH will send MassHealth a file with participants' Study IDs linked with a limited set of patient study data including, study arm, dates of Year 1 (baseline), Year 2 (intervention year 1), and Year 3 (intervention year 2) data collection, age group (in ten year increments), gender, race (White, Black, Asian, Other), ethnicity (Hispanic, Not Hispanic), self-reported smoking cessation medication use (varenicline, bupropion, nicotine replacement therapy) at Year 1 (baseline), Year 2 (intervention year 1), and Year 3 (intervention year 2), and self reported abstinence at baseline, year 1 and year 2.

MassHealth will link prescription fill data for smoking cessation medications (January 2015-June 2020) with the limited set of patient study data, but strip all study and the MassHealth IDs before returning the data to MGH. Specifically, MassHealth will create a new encrypted ID for each participant only, which will not be linkable with the main study IDs, thus deidentifying the data we receive and analyze. MassHealth will also replace medication fill dates with flags corresponding to which of the study year windows the medication was filled (year prior to

baseline, baseline-interventionY1, intervention Y1-Y2) and strip exact dates from the file. Thus, we will receive a deidentified file from MassHealth that contains the following information:

Encrypted ID
Coverage indicators (e.g., dual-eligibility, MassHealth plan type (e.g., MCO, FFS))
Death Flag (Y/N) during Post-intervention period
Claims for smoking cessation medications (i.e., varenicline, bupropion, NRT)
Indicator for fill date during either pre vs. post intervention window
National Drug Code (NDC)
Drug generic/brand name
Quantity filled
Days supply
New or refill indicator
Drug costs (e.g., Medicaid paid amount, Patient paid amount (i.e. co-pay))
Claim version / Claim denial flag
Prescribing provider

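### The returned MassHealth file lists study arm but no clinic code or cohort flag, so the claims comparison of AD with TAU cannot carry the clinic random effect that clinic randomisation calls for

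*Combined protocol and SAP*

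**What the plan says.** **Randomisation (section IV, Subject Enrollment).** For Cohort 1, "These clinics were randomized to receive AD to their clinicians or TAU". Within AD clinics, participants were then randomised to be offered a CHW or not. Cohort 2 participants were randomised individually to CHW or TAU. The statisticians add a field that "indicates, for each study ID, the clinic assignment (TAU or AD) and CHW assignment". Randomisation was "based on de-identified data provided by the psychiatric rehabilitation agencies about the primary care clinic and the study ID", so the statisticians have held clinic by study ID.

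**Claims data (same section).** The plan is to obtain "pharmacy claims data for all study participants who are covered by MassHealth". MGH sends study IDs with arm, survey dates, demographics, self-reported medication use and self-reported abstinence. MassHealth links the fills and removes both sets of IDs, and "MassHealth will create a new encrypted ID for each participant only, which will not be linkable with the main study IDs". The returned file is then itemised: coverage, death flag, claim details (prescribing provider among them), arm, age group, gender, race, ethnicity, and self-reported medication use and abstinence. Neither clinic nor cohort is listed.

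**Analysis (section VII).** Under Aim 1, section VII.2 plans two claims analyses: prescribing patterns of AD vs TAU providers, and fill rates across AD, AD+CHW, CHW and TAU. It names no model for either. For Hypothesis 1a and for self-reported prescriptions received and filled (Exploratory Aim 3) it names a clinic random effect. Section VII.1 says the Cohort 2 comparison can be held apart from the main three-arm analysis, and uses cohort as a factor in the combined analysis.

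**The concern.** Participants at one clinic share prescribers, and AD acts on those prescribers, so fills within a clinic are likely to be correlated. An AD vs TAU analysis that treats participants as independent overstates its information. The survey analyses can allow for this because clinic is available by study ID. The claims analysis cannot, because the specification of the data leaves clinic out and the new ID prevents adding it later. Silence about the model could be cured in the analysis; a missing field cannot.

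The cohort question is separate. Only Cohort 1 clinics were randomised to AD or no AD. If TAU arrives as a single label, Cohort 2 participants enter the AD vs TAU contrast without having been part of that randomisation, and for TAU the file allows neither separation by cohort nor cohort as a factor.

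According to the waiver request in section IV, the funder asked for these data, and their value is that they do not rest on self-report. Overstated precision would weaken them for that purpose.

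**Working it through.** **1. Fields.** The contrast needs fill (yes/no), arm, clinic and cohort for each covered participant. The returned list supplies the first two. Prescribing provider is a claim field: a participant with no fill has none, and no key from provider to clinic is described. It therefore gives no cluster for the zero category of a fill outcome. If arm has four levels, cohort follows for AD, AD+CHW and CHW. Only TAU is ambiguous.

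**2. Inputs.** The plan states no test level, power or ICC for claims, so it has no figure to reproduce.
- Cohort 1: 1165 − 155 = 1010 participants (section III).
- Clinics: 26–30 AD plus 13–15 TAU, so 39–45 (section III). Mean size is 1010/45 = 22.4 to 1010/39 = 25.9; I use 42 clinics, 1010/42 = 24.
- One third of clinics to TAU and half of AD-clinic participants to CHW (section VII.1): about 337 each in TAU, AD alone and AD+CHW. An AD clinic of 24 contributes 12 to AD alone.
- ICC: 0.03 and 0.07 are the abstinence values in section VII.4; 0.01 is an assumed low value.
- Assumed: a two-sided 5% test, and half coverage (12 per clinic) as a variant.

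**3. Formulas.** DE = 1 + (m − 1) × ICC in each arm, with m participants per clinic. For arms of equal size, the variance of the difference grows by the mean of the two DEs. When all AD-clinic participants are compared with TAU, m and hence DE are the same on both sides. The correct interval is √DE times the naive one. The true size of a naive test is 2 × (1 − Φ(1.96/√DE)).

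| Contrast | ICC | DE, TAU | DE, AD | Mean DE | Interval ratio | True size |
|---|---|---|---|---|---|---|
| AD alone vs TAU, 24 per clinic | 0.01 | 1.23 | 1.11 | 1.17 | 1.08 | 0.070 |
| | 0.03 | 1.69 | 1.33 | 1.51 | 1.23 | 0.111 |
| | 0.07 | 2.61 | 1.77 | 2.19 | 1.48 | 0.185 |
| AD alone vs TAU, 12 per clinic | 0.01 | 1.11 | 1.05 | 1.08 | 1.04 | 0.059 |
| | 0.03 | 1.33 | 1.15 | 1.24 | 1.11 | 0.078 |
| | 0.07 | 1.77 | 1.35 | 1.56 | 1.25 | 0.117 |
| All AD-clinic participants vs TAU, 24 per clinic | 0.01 | 1.23 | 1.23 | 1.23 | 1.11 | 0.077 |
| | 0.03 | 1.69 | 1.69 | 1.69 | 1.30 | 0.132 |
| | 0.07 | 2.61 | 2.61 | 2.61 | 1.62 | 0.225 |

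Over 22.4 to 25.9 per clinic, AD alone vs TAU ranges over 0.107–0.116 at ICC 0.03 and 0.177–0.195 at 0.07.

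**4. Simulation.** With 28 AD and 14 TAU clinics of 24, an assumed fill rate of 0.20 and 20,000 runs, ignoring clinic gave 0.072, 0.114 and 0.182 for AD alone vs TAU, and 0.078, 0.129 and 0.229 for all AD-clinic participants. In a second simulation (27 AD and 13 TAU clinics averaging 22.5), a clinic-level t test had size 0.050–0.058. The inflation therefore comes from leaving clinic out; the number of clinics is adequate.

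**5. Cohort share of a single TAU code.** Cohort 2 is split 1:1, so 155/2 ≈ 78 in TAU. Cohort 1 TAU is 1010/3 ≈ 337. The share is 78/(337 + 78) = 78/415 = 19%, before coverage. If TAU clinics hold 30% to 37% of Cohort 1 (303 to 374 participants), it is 20% to 17%.

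**The case against.** The strongest reply is that these are supplementary analyses. Section VII.2 introduces them as additional, says only that differences will be examined, and sets no test level. This stands: the true size above describes an assumed test. The narrowing of the intervals, however, needs no test.

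The first claims analysis concerns providers, and prescribing provider is returned, so prescribing patterns may be described by provider. This also stands, but it does not reach participants without a fill.

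The outgoing data are described as a "limited set of patient study data including, study arm, dates of Year 1 (baseline" and so on, which leaves room for an unlisted field. The returned file, however, is itemised, and its ID rules out a later merge.

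Privacy is a real constraint. Section IV requires cells of at least 10 for individual and combined data elements, and Cohort 1 admits clinics with only 3 participants. That limits a clinic code. It does not limit a cohort flag in the same way, and a standard-error correction needs no new field.

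A reader might infer that TAU is certainly a mixture of cohorts. The documents do not show how arm is coded in the file, so the 19% is conditional. A reader might also fault the timing, since the text speaks of "flags corresponding to which of the study year windows the medication was filled" while the field list has "Indicator for fill date during either pre vs. post intervention window". The cut of the binary flag should be stated, but the documents do not show that a different main window is needed. Making the last window the main one would discard time after randomisation in which AD is delivered.

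**Conclusion.** The point holds. As specified, the file cannot support a clinic random effect for claims-based fills in AD vs TAU, and no other allowance for clinic is stated. For AD alone vs TAU, the contrast in the four-arm list, the correct interval at 24 per clinic is 8%, 23% and 48% wider than the naive one at ICC 0.01, 0.03 and 0.07. A nominal 5% test has true size of about 7%, 11% and 18.5%; at half coverage, about 6%, 8% and 12%. These figures rest on equal clinic sizes, on abstinence ICCs standing in for fill ICCs, and on the assumed test level and coverage.

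Three stronger readings are not supported. The plan does not break a promise, since it never names a clinic random effect for claims. The largest figures (about 8%, 13% and 22.5%) belong to all AD-clinic participants vs TAU and should not be quoted for the four-arm contrast. The trial's main conclusions are not at risk: the primary outcome and the survey analyses have clinic available, and AD+CHW vs AD is randomised within clinics. This should be put right for a supplementary analysis and does not threaten the trial.

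**What to change.** 1. Add a cohort flag to the file MGH sends and have it returned, or code Cohort 1 TAU and Cohort 2 TAU separately. Restrict AD vs TAU fills to covered Cohort 1 participants.
2. State that standard errors of claims-based AD vs TAU contrasts will be inflated by a design effect, using the clinic ICC of survey-reported medication use, where clinic is known. With 42 clinics of 24, that ICC has a standard error of about 0.01–0.02, so report results over ICC 0.01–0.07.
3. If the data use agreement and the 10-person rule allow, add a masked or merged clinic code before linkage and fit a clinic random effect with small-sample degrees of freedom in place of item 2. Agree first how the rule applies. A clinic cell of 10 at an assumed 20% fill rate holds about 2 fillers. A separate reduced extract would not avoid the problem, because arm and fill pattern by drug and window would appear in both files and could rejoin some fillers.

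Cost: items 1 and 3 need an amended data request, item 3 also needs privacy review, and intervals become wider. Item 2 needs no new data. The protocol is dated September 2021 and the claims end in June 2020, so if the file has already been received, item 2 is the part that can be done without returning to MassHealth. It does not separate a pooled TAU group, which would then have to be reported as a limitation.
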